13.1.1.3 Documentation of Adverse Events

All AEs will be collected from the time the ICF is signed until the completion of study participation (Section 9.1.5).

All subjects' parents or legal guardians will be queried, using nonleading questions, about the occurrence of AEs at each study visit. When possible, a constellation of signs and/or symptoms will be identified as 1 overall event or diagnosis. All AEs for enrolled subjects will be recorded in the CRF and source document. The following data will be documented for each AE:

- Description of the event
- Classification of "serious" or "nonserious"
- Date of first occurrence and date of resolution (if applicable)
- Severity
- Causal relationship to study drug(s)
- Action taken
- Outcome
- Concomitant medication or other treatment given

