Activity: CFTR potentiator

Strength:

[figure not shown]
- 150 mg IVA
- 75 mg IVA

Study Duration For subjects who enroll in both Parts A and B, the total study duration is approximately 196 weeks from the Part A Day 1 Visit (96 weeks for the Part A Treatment Period, 96 weeks for the Part B Treatment Period, and 4 weeks for the Safety Follow-up Period).

Study Design This is a Phase 3, 2-part, multicenter, open-label extension safety study for subjects who completed the Treatment Period in the parent study (VX18-445-106 Part B) and meet eligibility criteria. The study design is shown in [Figure 2-1](#).

Subjects who complete Part A will have the opportunity to enroll in Part B for an additional 96 weeks.

Figure 2-1 Schematic of the Study Design

IVA: ivacaftor; TEZ: tezacaftor

Note: The parent study is VX18-445-106 Part B, a Phase 3 study investigating VX-445/TEZ/IVA in subjects 6 through 11 years of age. The figure is not drawn to scale.

^a Subjects whose Part B Day 1 Visit is on the same day or within 1 calendar day of the Part A Week 96 Visit do NOT have to repeat any Part B Day 1 assessments that were specified to be performed at the Part A Week 96 Visit. Subjects whose Part B Day 1 Visit is more than 1 calendar day after the Part A Week 96 Visit must complete all assessments specified for the Part A Week 96 AND Part B Day 1 Visits.

All subjects will receive VX-445/TEZ/IVA at weight-appropriate dosage levels for 96 weeks in Part A. In Part B, subjects will receive VX-445/TEZ/IVA at age- and weight-appropriate dosage levels for 96 weeks (Table 2-1).

Table 2-1 Treatment Period Dosages

Subject Weight	VX-445 Dosage	TEZ Dosage	IVA Dosage
Part A, subjects \geq6 years of age			
\geq 30 kg	200 mg qd	100 mg qd	150 mg q12h
<30 kg	100 mg qd	50 mg qd	75 mg q12h
Part B, subjects \geq6 to <12 years of age			
\geq 30 kg	200 mg qd	100 mg qd	150 mg q12h
<30 kg	100 mg qd	50 mg qd	75 mg q12h
Part B, subjects \geq12 years of age			
All weights	200 mg qd	100 mg qd	150 mg q12h

IVA: ivacaftor; q12h: every 12 hours; qd: once daily; TEZ: tezacaftor

Assessments **Safety:** AEs, clinical laboratory assessments, ECGs, vital signs, pulse oximetry, ophthalmologic examinations, and physical examinations

Efficacy and PD: spirometry, SwCl, CFQ-R, weight, height, multiple breath washout, and documentation of other events related to outcome (e.g., PEx, CF-related hospitalizations)

Other Assessments:

FE-1 and IRT will be measured to assess exocrine pancreatic function.

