6 STUDY OBJECTIVES

6.1 Primary Objective

To evaluate the long-term safety and tolerability of VX-445/TEZ/IVA in subjects with CF who are 6 years of age and older

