7 STUDY ENDPOINTS

7.1 Primary Endpoint

Safety and tolerability assessments based on adverse events (AEs), clinical laboratory values, ECGs, vital signs, pulse oximetry, and ophthalmologic examinations

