9 STUDY IMPLEMENTATION

9.1 Study Design

This is a Phase 3, 2-part, multicenter, open-label extension study for subjects who completed the Treatment Period in the parent study (VX18-445-106 Part B) and meet eligibility criteria. The study design is shown in [Figure 9-1](#).

Subjects who complete Part A will have the opportunity to enroll in Part B for an additional 96 weeks.

Study visits and assessments to be conducted are shown in [Table 3-1](#) and [Table 3-2](#). All visits will occur within the windows specified.

Figure 9-1 Schematic of the Study Design

IVA: ivacaftor; TEZ: tezacaftor

Note: The parent study is VX18-445-106 Part B, a Phase 3 study investigating VX-445/TEZ/IVA in subjects 6 through 11 years of age. The figure is not drawn to scale.

^a Subjects whose Part B Day 1 Visit is on the same day or within 1 calendar day of the Part A Week 96 Visit do NOT have to repeat any Part B Day 1 assessments that were specified to be performed at the Part A Week 96 Visit. Subjects whose Part B Day 1 Visit is more than 1 calendar day after the Part A Week 96 Visit must complete all assessments specified for the Part A Week 96 AND Part B Day 1 Visits.

All subjects will receive VX-445/TEZ/IVA at the weight-appropriate dosage levels for 96 weeks in Part A. In Part B, subjects will receive VX-445/TEZ/IVA at age- and weight-appropriate dosage levels for 96 weeks (Table 9-1).

Table 9-1 Treatment Period Dosages

Subject Weight	VX-445 Dosage	TEZ Dosage	IVA Dosage
Part A, subjects \geq6 years of age			
\geq 30 kg	200 mg qd	100 mg qd	150 mg q12h
<30 kg	100 mg qd	50 mg qd	75 mg q12h
Part B, subjects \geq6 to <12 years of age			
\geq 30 kg	200 mg qd	100 mg qd	150 mg q12h
<30 kg	100 mg qd	50 mg qd	75 mg q12h
Part B, subjects \geq12 years of age			
All weights	200 mg qd	100 mg qd	150 mg q12h

IVA: ivacaftor; q12h: every 12 hours; qd: once daily; TEZ: tezacaftor

Note: Study drug administration is described in Section 9.6.

Part A:

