Subjects weighing \geq 30 kg at the Part A Day 1 Visit will receive 200 mg VX-445 once daily (qd)/100 mg TEZ qd/150 mg IVA every 12 hours (q12h) for the duration of the study. Subjects weighing <30 kg at the Part A Day 1 Visit will receive 100 mg VX-445 qd/50 mg TEZ qd/75 mg IVA q12h. If a subject enters the current study weighing <30 kg and subsequently weighs \geq 30 kg at 2 consecutive clinic visits, the dose will be adjusted to the higher dose of 200 mg VX-445 qd/100 mg TEZ qd/150 mg IVA q12h for the remainder of the study, starting with the second visit where subject's weight is \geq 30 kg.

Part B:

In Part B, subjects will receive 200 mg VX-445 qd/100 mg TEZ qd/150 mg IVA q12h if they meet any of the following criteria:

- Subject is ≥ 12 years of age
- Subject received 200 mg VX-445 qd/100 mg TEZ qd/150 mg IVA q12h in Part A
- Subject is ≥ 30 kg on Part B Day 1

All other subjects <12 years of age and <30 kg will receive 100 mg VX-445 qd/50 mg TEZ qd/75 mg IVA q12h until either:

- The subject weighs ≥ 30 kg at 2 consecutive clinic visits in Part B, or
- The subject turns 12 years of age

Once either of the above criteria are met, the subject will receive 200 mg VX-445 qd/100 mg TEZ qd/150 mg IVA q12h for the remainder of the study.

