13.1.1.2 Clinically Significant Assessments

Study assessments including laboratory tests, ECGs, PEs, and vital signs will be assessed and those deemed to have clinically significant worsening from baseline will be documented as an AE. When possible, a clinical diagnosis for the study assessment will be provided, rather than the abnormal test result alone (e.g., urinary tract infection, anemia). In the absence of a diagnosis, the abnormal study assessment itself will be listed as the AE (e.g., bacteria in urine or decreased hemoglobin).

An abnormal study assessment is considered clinically significant if the subject has 1 or more of the following:

- Concomitant signs or symptoms related to the abnormal study assessment
- Further diagnostic testing or medical/surgical intervention
- A change in the dose of study drug or discontinuation from the study

Repeat testing to determine whether the result is abnormal, in the absence of any of the above criteria, does not necessarily meet clinically significant criteria. The determination of whether the study assessment results are clinically significant will be made by the investigator.

A laboratory value that is Grade 4 will not automatically be an SAE. A Grade 4 laboratory value will be an SAE if the subject's clinical status indicates a life-threatening AE.

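### Protocol 13.1.1.3 names only parents or legal guardians as respondents to the adverse event query, although a substantial share of subjects pass 12 on study; symptom-type events may be under-recorded in older subjects

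*Protocol*

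**What the plan says.** Protocol 13.1.1.3 sets both the collection period and the respondent. On the period: "All AEs will be collected from the time the ICF is signed until the completion of study participation". On the respondent: "All subjects' parents or legal guardians will be queried, using nonleading questions, about the occurrence of AEs at each study visit". This is the only instruction in either document on whom to ask about AEs, and it does not vary with age.

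The parent study is described in the Figure 9-1 note as "a Phase 3 study investigating VX-445/TEZ/IVA in subjects 6 through 11 years of age". For subjects who take part in both Parts, the synopsis states that "the total study duration is approximately 196 weeks from the Part A Day 1 Visit". The primary objective concerns long-term safety "in subjects with CF who are 6 years of age and older". Protocol 9.1 plans for subjects who grow older on study: Part B has a dosage row for those aged 12 and over, and one trigger for a dosage change is "The subject turns 12 years of age".

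The primary endpoint (Protocol 7.1) is "Safety and tolerability assessments based on adverse events (AEs), clinical laboratory values, ECGs, vital signs, pulse oximetry, and ophthalmologic examinations". AEs are one of its six components.

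**The concern.** The respondent rule suits a 6-year-old. It is less suited to a subject of 14 or 15, who may have symptoms that a parent neither notices nor is told about. Part B makes dosage depend on reaching 12, but AE elicitation does not change with age.

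Elsewhere the protocol does name the subject: for hospitalizations (11.3.6.2), for the CFQ-R (11.3.5, subject or caregiver) and for reporting pregnancy (11.5.6.2). A site could therefore take the AE rule as deliberate and put the question to the parent alone.

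What is at stake is the completeness of the AE data. The SAP reports AE counts, percentages and exposure-adjusted rates over Parts A and B pooled (3.1, 10.4.2.1). Rash is an event of special interest, summarized by severity, duration and time to onset (10.4.2.9.1). For events outside the CTCAE, severity is graded by discomfort and interference with activities (Protocol 13.1.1.4), which the subject is usually best placed to describe.

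**Working it through.** **Duration.** The synopsis figure reproduces: 96 + 96 + 4 = 196 weeks, and 196 × 7 / 365.25 = 3.76 years. Treatment alone is 192 weeks, or 192 × 7 / 365.25 = 3.68 years. Both apply only to subjects who enter Part B.

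**Inputs for age.** Age at parent-study entry is 6 through 11 years, taken as 6 to under 12 (Figure 2-1 and 9-1 notes; SAP 7.1). Protocol 8 describes the parent study as being in subjects 6 years and older; the narrower range is used here. The documents give neither the age distribution nor the length of the parent study. Both are assumptions: parent length 0 to 24 weeks, and entry ages either uniform or triangular with the peak at the young end, the middle or the old end.

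**Share aged 12 or older.** Let t be the years from parent-study entry.

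- Uniform: t / 6.
- Young-weighted: (t / 6)².
- Old-weighted: 1 − (1 − t / 6)².
- Middle-weighted (peak at 9): t² / 18 for t up to 3, and 1 − (6 − t)² / 18 beyond that.

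At Part A Week 96, t = 96 × 7 / 365.25 = 1.84 with no parent-study time, or 120 × 7 / 365.25 = 2.30 with 24 weeks. At Part B Week 96, t = 3.68 or 216 × 7 / 365.25 = 4.14.

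| Entry ages | Parent length | Part A Week 96 | Part B Week 96 |
|---|---|---|---|
| Uniform | 0 weeks | 1.84 / 6 = 31% | 3.68 / 6 = 61% |
| Uniform | 24 weeks | 2.30 / 6 = 38% | 4.14 / 6 = 69% |
| Young-weighted | 0 weeks | 9% | (3.68 / 6)² = 38% |
| Middle-weighted | 0 weeks | 19% | 70% |
| Middle-weighted | 24 weeks | 29% | 81% |
| Old-weighted | 24 weeks | 62% | 1 − (1 − 0.69)² = 90% |

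SAP 7.2 gives 64 enrolled. If all stayed to Part B Week 96, the uniform case gives 64 × 0.613 = 39 to 64 × 0.690 = 44 subjects aged 12 or older.

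**Oldest age.** 12 + 3.68 = 15.7 years, or 12 + 4.14 = 16.1 years with 24 parent-study weeks.

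**Which events depend on the parent's answer.** Several AE routes bypass the parent query:

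- For laboratory tests, ECGs, physical examinations and vital signs, "those deemed to have clinically significant worsening from baseline will be documented as an AE" (13.1.1.2).
- Clinically significant ophthalmologic findings are AEs (11.5.5).
- Subjects are themselves asked about hospitalizations, and safety reporting follows (11.3.6.2).
- New or changed antibiotics for sinopulmonary signs or symptoms are documented (11.3.6.1), and medications and treatments are reviewed continuously (Tables 3-1 and 3-2).

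What remains is symptoms that lead to no admission and no treatment, and leave no finding at a scheduled assessment. A headache, or a mild rash that clears between visits, would be an example. Full physical examinations are scheduled only at Day 1, Week 96 and early termination in each Part.

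**Size of the shortfall.** The documents contain no under-reporting rate, so the number of missed events cannot be calculated.

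**The case against.** The strongest reply is that the sentence sets a minimum, not an exclusion. It says whom the site must ask. It does not forbid asking the subject, and the same section requires all AEs to be collected whatever their source. Protocol 11.5.1 leaves detail to CRF guidelines and training that are not among these documents and may cover the point. Every subject is still under 18 at Part B Week 96, so a guardian query is a reasonable universal floor. All of this stands. It limits the point to the wording of the rule and the narrow class of events described above. It does not remove it, because a site that follows the text literally need not ask the subject.

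Four stronger readings are tempting, and the documents do not support them.

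- A reader might infer that events are in fact missed, and increasingly so with age. That is a plausible risk, but nothing here shows or sizes it.
- A reader might infer that a falling AE rate over the extension would be misread as better tolerability. The SAP plans no AE table by age or time interval and pools Parts A and B. AE data may be displayed beside the parent study's (10.4.2), but a trend would have to come from informal comparison of tables.
- Of the 48 four-weekly contacts after Day 1, 31 are by telephone (15 in Part A, 16 in Part B). A reader might infer that the parent alone is spoken to at these. No text says who takes the call.
- A reader might infer that the rule was overlooked when Part B was added. The previous protocol text of this section is not available, so its drafting history is unknown.

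**Conclusion.** The point holds as a correctable weakness in one sentence of the protocol. The only named respondents to the AE query are parents or guardians, with no provision for the subject, in a study where a substantial share of subjects pass 12. By Part B Week 96 that share is about 61% to 69% under uniform entry ages and a parent study of 0 to 24 weeks, and 38% to 90% across the skewed distributions tried. These figures assume that subjects enter Part B and stay to its end.

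The consequence is possible under-recording, in older subjects, of symptom-type events that are not hospitalized, not treated and not found at scheduled assessments. It bears on the AE component of the primary endpoint, not on the laboratory, ECG, vital sign, oximetry or eye components. Its size is unknown. Safety is analysed descriptively, so no test result is at risk.

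**What to change.** In Protocol 13.1.1.3, change the respondents named in the sentence to subjects (as developmentally appropriate, and always from 12 years of age) and their parents or legal guardians. Keep the nonleading form of the question, and state that a study visit means clinic or telephone. Protocol 9.1.4 already counts telephone contacts as study visits, so that last part only makes the meaning explicit. An informant field on the AE page (subject, parent or both) is optional.

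The cost is a one-sentence amendment, matching text in the CRF guidelines and a little time at each contact. The sponsor must submit the amendment to regulators (13.2.3), and the optional field would also need a change to the data capture system.

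The downside is statistical. Enrolment is already reported (SAP 7.2), so the change falls mid-study and recorded AE rates may rise slightly afterwards, inside the pooled Part A and Part B data. The date of the change should be noted when those rates are interpreted. An informant field would make the break visible but would not remove it. The change also does not ensure that a symptom kept from a parent is reported, because it does not require the subject to be asked separately.

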13.1.1.4 Adverse Event Severity

The investigator will determine and record the severity of all serious and nonserious AEs. The guidance available at the following website will be consulted: Common Terminology Criteria for Adverse Events (CTCAE), Version 5.0, Cancer Therapy Evaluation Program, http://ctep.cancer.gov/protocolDevelopment/electronic_applications/ctc.htm (Accessed February 2019). AEs of CTCAE Grades 4 and 5 will be documented as "life-threatening." When considering the severity of an AE in a pediatric subject, the investigator will consider that reference ranges for pediatric clinical laboratory parameters may differ from those in the CTCAE. The severity of an AE described by a term that does not appear in the CTCAE will be determined according to the definitions in Table 13-1.

Table 13-1 Grading of AE Severity

Classification	Definition
Mild (Grade 1)	Mild level of discomfort and does not interfere with regular activities
Moderate (Grade 2)	Moderate level of discomfort and significantly interferes with regular activities
Severe (Grade 3)	Significant level of discomfort and prevents regular activities
Life-threatening (Grade 4)	Any adverse drug event that places the subject, in the view of the investigator, at immediate risk of death

AE: adverse event

13.1.1.5 Adverse Event Causality

Every effort will be made by the investigator to assess the relationship of the AE, if any, to the study drug(s). Causality will be classified using the categories in [Table 13-2](#).

Table 13-2 Classifications for AE Causality

Classification	Definition
Related	There is an association between the event and the administration of investigational study drug, a plausible mechanism for the event to be related to the investigational study drug and causes other than the investigational study drug have been ruled out, and/or the event reappeared on re-exposure to the investigational study drug.
Possibly related	There is an association between the event and the administration of the investigational study drug and there is a plausible mechanism for the event to be related to investigational study drug, but there may also be alternative etiology, such as characteristics of the subject's clinical status or underlying disease.
Unlikely related	The event is unlikely to be related to the investigational study drug and likely to be related to factors other than investigational study drug.
Not related	The event is related to an etiology other than the investigational study drug (the alternative etiology will be documented in the subject's medical record).

AE: adverse event

13.1.1.6 Study Drug Action Taken

The investigator will classify the study drug action taken with regard to the AE. The action taken will be classified according to the categories in [Table 13-3](#).

Table 13-3 Classifications for Study Drug Action Taken With Regard to an AE

Classification ^a	Definition
Dose not changed	Study drug dose not changed in response to an AE
Dose reduced	Study drug dose reduced in response to an AE
Drug interrupted	Study drug administration interrupted in response to an AE
Drug withdrawn	Study drug administration permanently discontinued in response to an AE
Not applicable	Action taken regarding study drug administration does not apply. “Not applicable” will be used in circumstances such as when the investigational treatment had been completed before the AE began and no opportunity to decide whether to continue, interrupt, or withdraw treatment is possible.

AE: adverse event

^a Refer to Sections [9.7](#) and [9.8](#) for directions regarding what drug actions are permitted per protocol.

13.1.1.7 Adverse Event Outcome

An AE will be followed until the investigator has determined and provided the final outcome. The outcome will be classified according to the categories in [Table 13-4](#).

Table 13-4 Classifications for Outcome of an AE

Classification	Definition
Recovered/resolved	Resolution of an AE with no residual signs or symptoms
Recovered/resolved with sequelae	Resolution of an AE with residual signs or symptoms
Not recovered/not resolved (continuing)	Either incomplete improvement or no improvement of an AE, such that it remains ongoing
Fatal	Outcome of an AE is death. “Fatal” will be used when death is at least possibly related to the AE.
Unknown	Outcome of an AE is not known (e.g., a subject lost to follow-up)

AE: adverse event

13.1.1.8 Treatment Given

The investigator ensures adequate medical care is provided to subjects for any AEs, including clinically significant laboratory values related to study drug. In addition, the investigator will describe whether any treatment was given for the AE. “Yes” is used if any treatment was given in response to an AE, and may include treatments such as other medications, surgery, or physical therapy. “No” indicates the absence of any kind of treatment for an AE.

13.1.2 Serious Adverse Events

13.1.2.1 Definition of a Serious Adverse Event

An SAE is any AE that meets any of the following outcomes:

- Fatal (death, regardless of cause, that occurs during participation in the study or occurs after participation and is suspected of being a delayed toxicity due to administration of the study drug)
- Life-threatening, such that the subject was at immediate risk of death from the reaction as it occurred
- Inpatient hospitalization or prolongation of hospitalization
- Persistent or significant disability/incapacity (disability is defined as a substantial disruption of a person’s ability to conduct normal life functions)
- Congenital anomaly or birth defect
- Important medical event that, based upon appropriate medical judgment, may jeopardize the subject or may require medical or surgical intervention to prevent 1 of the outcomes listed above (e.g., an allergic bronchospasm requiring intensive treatment in an emergency room or at home)

If a subject has a hospitalization or procedure (e.g., surgery) for an event or condition that occurred before the subject signed the ICF, and the hospitalization or procedure was planned before the subject signed the ICF, the hospitalization or procedure will not be considered to

indicate an SAE, unless an AE caused the hospitalization or procedure to be rescheduled sooner or to be prolonged relative to what was planned. In addition, hospitalizations clearly not associated with an AE (e.g., social hospitalization for purposes of respite care) will not be considered to indicate an SAE.

Clarification will be made between the terms “serious” and “severe” because they are not synonymous. The term “severe” is often used to describe the intensity (severity) of a specific event, as in mild, moderate, or severe myocardial infarction. The event itself, however, may be of relatively minor medical significance, such as a severe headache. This is not the same as “serious”, which is based on subject/event outcome or action described above, and is usually associated with events that pose a threat to a subject’s life or functioning. Seriousness, not severity, serves as a guide for defining expedited regulatory reporting obligations.

